8.4.5.2 Dose Modification for Peripheral Neuropathy and Neutropenia

Peripheral neuropathy should be managed using a combination of dose delay and reduction to 2/3 of the initial dose:

- For new or worsening CTCAE grade 2 or 3 neuropathy: hold dose until neuropathy improves to CTCAE grade ≤ 1, and then restart at 2/3 of the initial dose until end of trial treatment.
- For CTCAE grade 4 peripheral neuropathy: stop dosing and the patient should be withdrawn from treatment.

Neutropenia should be managed by dose delays and dose reductions:

- Dosing should be held for CTCAE grade 3 or 4 neutropenia until resolution to CTCAE grade ≤ 2.
- Growth factor support should be considered for subsequent cycles in patients who experience CTCAE grade 3 or 4 neutropenia.
- In patients with recurrent CTCAE grade 4 neutropenia despite the use of growth factors, discontinuation or dose reduction of trial drug to 2/3 of the initial dose until end of trial treatment may be considered after discussion with the sponsor Medical Officer.

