8.3.4 Withdrawal and Replacement of Patients

8.3.4.1 Criteria for Patient Withdrawal from Treatment

Patients will be withdrawn from treatment for the following reasons:

- DLT/DLT-equivalent events (see Section 8.4.8 for specification, exception and dose modifications).
- > 2 dose reductions due to recurrent toxicities possibly related to tisotumab vedotin (HuMax-TF-ADC) (see Sections 8.4.5.1, 8.4.5.2, and 8.4.5.3).
- CTCAE grade \geq 3 macular-papular skin rash.
- CTCAE grade 1 treatment-related bullous dermatitis or skin bullae (blister) ≥ 0.5 cm.
- Recurrent CTCAE grade 4 neutropenia may be withdrawn, see Section 8.4.5.2.
- CTCAE grade 3 QTcF interval prolongation (≥ 501 msec on at least two separate ECGs).
- First recurrence of CTCAE grade ≥ 3 conjunctivitis (despite dose reduction, see Section 8.4.5.3)
- Third recurrence of CTCAE grade ≤ 2 keratitis (despite dose reductions, see Section 8.4.5.3)
- First occurrence of CTCAE grade \geq 3 keratitis
- Ophthalmological evaluation reveals conjunctival/corneal scarring
- Any grade of symblepharon
- Any grade of fluorescent patches or conjunctival ulceration that does not stabilize or improve after dose reduction
- Any dose delay related to ocular toxicity exceeding 12 weeks

Final 5.0 (incorporating Protocol Amendment 4) 06 Jul 2017

- Dose delay of more than two weeks due to toxicity possibly related to tisotumab vedotin (HuMax-TF-ADC) (except for dose delays due to neuropathy, skin rash, keratitis and conjunctivitis)*.
- Pregnancy.
- Patient choice.
- Investigator or sponsor decision.
- * The exception is due to the fact that decrease to CTCAE grade 1 intensity for neuropathy, skin rash, keratitis and conjunctivitis may last for more than two weeks.

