8.4.5 Dose Modification and Mitigation Plans

Dose modifications should be preapproved by the sponsor Medical Officer. Below the dose modification and mitigation plans are specified according to the once q3wk treatment scheme:

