8.4.5.3 Dose Modifications and Mitigation Plan for Ocular Adverse Events

Events of conjunctivitis and keratitis have been reported in patients treated with tisotumab vedotin (HuMax-TF-ADC). To prevent occurrence and ensure appropriate handling, events should be prevented and managed as described below.

Final 5.0 (incorporating Protocol Amendment 4) 06 Jul 2017

Preventive measures for all patients:

- Use of preservative-free lubricating eye drops from the start of trial treatment until the end of treatment.
- Avoid use of contact lenses while treated with tisotumab vedotin (HuMax-TF-ADC).
- Use of refrigerator-based eye cooling pads during infusion, e.g. THERA PEARL Eye Mask or similar. To be applied immediately before infusion in accordance with the instructions provided with the eye cooling pads.
- Administration of local ocular vasoconstrictor before infusion (brimonidine tartrate 0.2% eye drops or similar, 3 drops in each eye immediately prior to start of infusion; otherwise to be used in accordance with the product prescribing information). If the patient does not tolerate ocular vasoconstrictors due to adverse reactions, continued treatment with these may be stopped at the discretion of the investigator and following discussion with the Genmab Medical Officer.
- Application of steroid eye drops for 3 days from the day of infusion (dexamethasone 0.1% eye drops or equivalent, 1 drop in each eye 3 times daily for 3 days [first drop to be given before start of infusion], otherwise to be used in accordance to product prescribing information).

In case of any ocular symptoms:

Conjunctivitis:

Grading: All events of conjunctivitis should be graded according to both:

- Ophthalmological grading based on the objective eye-examination findings performed by the ophthalmologist.
- CTCAE grading system based on National Cancer Institute Common Terminology Criteria for Adverse Events (NCI-CTCAE) version 4.03 (NCI-CTCAE v4.03, 2010) assessed by the investigator.

Dose delay and dose modification:

- CTCAE grade 1 conjunctivitis: Hold dosing until the event is managed effectively by topical treatment initiated by the ophthalmologist (according to treatment guidelines below). When the event is managed effectively the patient can be re-treated with the same dose of trial drug as being administered prior to the event onset.

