 - In case of 3^{rd} occurrence of keratitis CTCAE grade ≤ 2 , the patient must permanently discontinue treatment with trial drug.
- CTCAE grade ≥ 3 keratitis: The patient must permanently discontinue treatment with trial drug.

Final 5.0 (incorporating Protocol Amendment 4) 06 Jul 2017

Conjunctival ulceration:

If an ophthalmological evaluation reveals fluorescent patches or conjunctival ulceration of any grade:

- Hold dose until conjunctivitis/conjunctival ulceration is managed effectively by topical treatment (according to treatment guidelines below). When the event is managed effectively, dosing of trial drug can be resumed at a reduced dose (please refer to dose modification scheme below).
- o If symptoms do not stabilize/improve after dose reduction, the patient must permanently discontinue treatment with trial drug.

Treatment guidelines

_	
Ocular symptom	Treatment guideline (The length of treatment should be decided by the local ophthalmologist)
Conjunctivitis: CTCAE grade 1	The local ophthalmologist should prescribe frequent dosing of preservative-free topical steroid drops
Conjunctivitis: CTCAE grade 2	The local ophthalmologist should prescribe frequent dosing (every 2nd hour) of preservative-free topical steroid drops in conjunction with preservative free antibiotic prophylaxis such as chloramphenicol
Conjunctivitis: CTCAE grade 3	The local ophthalmologist should prescribe frequent dosing (every 2nd hour) of preservative-free topical steroid drops in conjunction with preservative free antibiotic prophylaxis such as chloramphenicol
Keratitis: CTCAE grade 1	The local ophthalmologist should prescribe frequent dosing of preservative-free topical steroid drops
Keratitis: CTCAE grade 2	The local ophthalmologist should prescribe frequent dosing (every 2nd hour) of preservative-free topical steroid drops in conjunction with preservative free antibiotic prophylaxis such as chloramphenicol
Conjunctival ulceration: any grade	The local ophthalmologist should prescribe frequent dosing (every 2nd hour) of preservative-free topical steroid drops in conjunction with preservative free antibiotic prophylaxis such as chloramphenicol

Final 5.0 (incorporating Protocol Amendment 4)
06 Jul 2017

Dose modification scheme:

Previous dose of tisotumab vedotin	Reduced dose of tisotumab vedotin	
2.0 mg/kg	1.3 mg/kg	
1.3 mg/kg	0.9 mg/kg	
0.9 mg/kg	0.9 mg/kg*	

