^{*}If the patient is already being treated with tisotumab vedotin (HuMax-TF-ADC) 0.9 mg/kg every 3rd week, the dose of tisotumab vedotin (HuMax-TF-ADC) should not be reduced further.

Trial drug discontinuation criteria for ocular toxicity:

Treatment with trial drug must be permanently discontinued in case of:

- First recurrence of CTCAE grade ≥ 3 conjunctivitis (despite dose reduction)
- Third recurrence of CTCAE grade ≤ 2 keratitis (despite dose reductions)
- First occurrence of CTCAE grade \geq 3 keratitis
- Ophthalmological evaluation reveals conjunctival/corneal scarring
- Any grade of symblepharon
- Any grade of fluorescent patches or conjunctival ulceration that does not stabilize or improve after dose reduction
- Any dose delay related to ocular toxicity exceeding 12 weeks

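### The neuropathy restart dose in Section 8.4.5.2 is not capped at the dose held at onset, so read literally it can raise the dose of a patient already reduced for another toxicity

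*Protocol*

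**What the plan says.** Section 8.4.5 opens by setting the scheme to which the rules apply: "Below the dose modification and mitigation plans are specified according to the once q3wk treatment scheme". Section 8.4.1 sets the q3wk dose at 2.0 mg/kg, whatever was given before.

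Section 8.4.5.2 introduces the neuropathy rule with "Peripheral neuropathy should be managed using a combination of dose delay and reduction to 2/3 of the initial dose". The grade 2 or 3 bullet then says to hold dosing until grade 1 or better "and then restart at 2/3 of the initial dose until end of trial treatment". Neither sentence mentions the dose the patient was receiving at onset. For recurrent grade 4 neutropenia the section uses the same base, but as an option alongside discontinuation, and only once the Medical Officer has been consulted: "dose reduction of trial drug to 2/3 of the initial dose until end of trial treatment may be considered".

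Two neighbouring sections can lower the dose first:

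- Section 8.4.5.3 (ocular events) steps from 2.0 to 1.3 to 0.9 mg/kg and allows dosing to continue at 0.9. It works from the dose actually being given. Grade 1 conjunctivitis: "the patient can be re-treated with the same dose of trial drug as being administered prior to the event onset". The scheme's left-hand column is headed "Previous dose of tisotumab vedotin". Its footnote covers the lowest level explicitly: "If the patient is already being treated with tisotumab vedotin (HuMax-TF-ADC) 0.9 mg/kg every 3rd week".
- Section 8.4.5.1 (skin) puts a patient with a vesicular reaction on half dose for the rest of the treatment period.

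Section 8.3.4.1 withdraws patients whose dosing is delayed more than two weeks for related toxicity, "except for dose delays due to neuropathy, skin rash, keratitis and conjunctivitis".

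**The concern.** Two thirds of the initial dose is a reduction only for a patient who is still above that level. For a patient already below it, the written instruction is to restart higher than before, after a new toxicity has appeared. The ocular section avoids this by working from the previous dose; the neuropathy rule does not.

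The patients affected would be those with repeated ocular toxicity, or with a vesicular skin reaction, who then also develop neuropathy. Amendment 4 was itself an urgent safety measure for severe ocular toxicity, so a rule that can undo an ocular reduction deserves correction even if the sequence is uncommon.

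**Working it through.** **Inputs.** Initial q3wk dose 2.0 mg/kg (8.4.1). Restart fraction 2/3 (8.4.5.2). Ocular steps 1.3 and 0.9 mg/kg (8.4.5.3). Half dose after a vesicular reaction, taken as half of 2.0 = 1.0 mg/kg (8.4.5.1). At most nine cycles (8.1). The protocol gives no mg/kg figure for the neuropathy restart.

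**The plan's own ocular steps.** 2/3 × 2.0 = 1.333, which rounds to the stated 1.3. 2/3 × 1.3 = 0.867 (or 4/9 × 2.0 = 0.889), which rounds to the stated 0.9. The ocular scheme is therefore two successive two-thirds steps, each from the previous dose. The neuropathy rule is a single two-thirds step, always from the initial dose.

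**Restart compared with dose held at onset.** Change = restart dose / dose held − 1, with the restart at 1.3 (rounded) or 1.333 (unrounded).

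| Dose held (mg/kg) | Restart 1.3 | Restart 1.333 | With a cap at the dose held |
|---|---|---|---|
| 2.0 | −35.0% | −33.3% | −35.0% to −33.3% |
| 1.3 (one ocular reduction) | 0.0% | +2.6% | 0% |
| 1.0 (vesicular reaction, half dose) | +30.0% | +33.3% | 0% |
| 0.9 (two ocular reductions) | +44.4% | +48.1% | 0% |

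**Can the sequences occur?** Two grade 2 conjunctivitis events, or two keratitis events of grade 2 or lower, bring a patient to 0.9 mg/kg with dosing allowed to continue. Delays for neuropathy, keratitis and conjunctivitis are exempt from the two-week withdrawal rule, so the patient can still be on treatment. On the skin route, a patient who recovers in time stays on half dose and can later develop neuropathy. The skin rule and the neuropathy rule then each fix a dose through to the end of treatment, and no text says which prevails.

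**Upper bound on the ocular route.** Cycle 1 at 2.0, cycle 2 at 1.3, cycle 3 at 0.9, neuropathy, restart at cycle 4. Cycles 4 to 9 are 6 doses: 6 × 0.9 = 5.4 mg/kg if held, 6 × 1.3 = 7.8 or 6 × 1.333 = 8.0 mg/kg if restarted as written. The excess is at most 2.4 to 2.6 mg/kg.

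**Sensitivity to the meaning of initial dose.** For a patient switched from 1.2 mg/kg 3q4wk, the term could be read as 1.2. Then 2/3 × 1.2 = 0.8 mg/kg, and 0.8/0.9 − 1 = −11.1%, so there is no rise.

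**The case against.** The strongest reply is that the section as a whole does not direct an increase. The bullet carries out a step that the lead-in calls a reduction, and going from 0.9 to 1.3 mg/kg is not one. Other provisions also stand in the way:

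- Section 8.4.5 asks for Medical Officer preapproval of dose modifications.
- The synopsis and Section 8.1 allow a reduced dose at the treating physician's discretion, given the patient's toxicity profile and with Medical Officer agreement. A patient could be kept at 0.9 mg/kg this way.
- Section 8.3.4.1 withdraws patients after more than two dose reductions for recurrent related toxicities, and cross-refers to 8.4.5.1, 8.4.5.2 and 8.4.5.3. If counted across toxicities, the neuropathy step would be the third and the patient would leave treatment.

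Much of this stands: an actual rise is unlikely. But none of these provisions is a cap. The first two rely on someone departing from the written restart dose. The third is open to argument, because a first neuropathy is not plainly a recurrent toxicity and a move up to 1.33 is not a reduction. It also cannot reach the skin route, where one earlier reduction plus the neuropathy step makes two, not more than two.

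Four stronger readings might be inferred, and the documents do not support them:

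- *The protocol intends an escalation.* The lead-in shows the opposite.
- *The neutropenia bullet has the same fault.* It shares the base, but it is optional and permits only a reduction or discontinuation, so it cannot mandate a rise.
- *Once raised, the dose stays raised.* Under 8.4.5.3 a further grade 2 conjunctivitis brings dosing back to 0.9 mg/kg, and a third keratitis of grade 2 or lower ends treatment. Six raised doses is therefore an upper bound.
- *A patient at 1.3 mg/kg is wrongly left unreduced.* Neuropathy may be meant to have a single reduced level.

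**Conclusion.** The neuropathy rule in Section 8.4.5.2 is wrong as written, and the point is minor. It fixes a restart dose without saying that a lower dose already in force prevails. Followed literally, it raises the dose by 44% to 48% from 0.9 mg/kg and by 30% to 33% from 1.0 mg/kg, against the rule's own stated purpose.

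These figures assume that the initial dose means the 2.0 mg/kg q3wk dose, which the opening of Section 8.4.5 supports but the protocol does not define for switched patients. They also assume that half dose means half of 2.0. The documents give no frequency for either sequence, so no expected number of affected patients can be stated.

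**What to change.** In the neuropathy lead-in and the grade 2 or 3 bullet of Section 8.4.5.2, change the restart dose to: *2/3 of the initial q3wk dose (1.3 mg/kg), or the dose held at onset if lower*. A restart after neuropathy then never exceeds the dose held at onset, as the last column of the table shows. Naming the q3wk dose also settles the base for switched patients. The same wording can go into the neutropenia bullet for consistency, though nothing there requires it. Whether a patient already at 1.3 mg/kg or below should stay, step down further or stop is for the sponsor to decide.

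The cost is one clause in two places, or three with the neutropenia bullet, and no new patients, visits or procedures. Because it changes a dosing rule, it needs a protocol amendment with the written regulatory and ethics approvals described in Section 15.2, and it can be carried in the next one.

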8.4.5.3 Dose Modifications and Mitigation Plan for Ocular Adverse Events

Events of conjunctivitis and keratitis have been reported in patients treated with tisotumab vedotin (HuMax-TF-ADC). To prevent occurrence and ensure appropriate handling, events should be prevented and managed as described below.

Final 5.0 (incorporating Protocol Amendment 4) 06 Jul 2017

Preventive measures for all patients:

- Use of preservative-free lubricating eye drops from the start of trial treatment until the end of treatment.
- Avoid use of contact lenses while treated with tisotumab vedotin (HuMax-TF-ADC).
- Use of refrigerator-based eye cooling pads during infusion, e.g. THERA PEARL Eye Mask or similar. To be applied immediately before infusion in accordance with the instructions provided with the eye cooling pads.
- Administration of local ocular vasoconstrictor before infusion (brimonidine tartrate 0.2% eye drops or similar, 3 drops in each eye immediately prior to start of infusion; otherwise to be used in accordance with the product prescribing information). If the patient does not tolerate ocular vasoconstrictors due to adverse reactions, continued treatment with these may be stopped at the discretion of the investigator and following discussion with the Genmab Medical Officer.
- Application of steroid eye drops for 3 days from the day of infusion (dexamethasone 0.1% eye drops or equivalent, 1 drop in each eye 3 times daily for 3 days [first drop to be given before start of infusion], otherwise to be used in accordance to product prescribing information).

In case of any ocular symptoms:

Conjunctivitis:

Grading: All events of conjunctivitis should be graded according to both:

- Ophthalmological grading based on the objective eye-examination findings performed by the ophthalmologist.
- CTCAE grading system based on National Cancer Institute Common Terminology Criteria for Adverse Events (NCI-CTCAE) version 4.03 (NCI-CTCAE v4.03, 2010) assessed by the investigator.

Dose delay and dose modification:

- CTCAE grade 1 conjunctivitis: Hold dosing until the event is managed effectively by topical treatment initiated by the ophthalmologist (according to treatment guidelines below). When the event is managed effectively the patient can be re-treated with the same dose of trial drug as being administered prior to the event onset.
- CTCAE grade 2 conjunctivitis: Hold dosing. Topical treatment should be initiated by the ophthalmologist (according to treatment guidelines below). When the event has improved to ≤ CTCAE grade 1, dosing of trial drug can be resumed at a reduced dose (please refer to dose modification scheme below).
 - o In case of recurrence of conjunctivitis CTCAE grade 2 the patient should hold dosing and topical treatment should be initiated by the ophthalmologist (according to treatment guidelines below). When the event is CTCAE grade ≤ 1, dosing of trial

Final 5.0 (incorporating Protocol Amendment 4)
06 Jul 2017

drug can be resumed at a further reduced dose (please refer to dose modification scheme below).

- If the conjunctivitis recurs again at CTCAE grade 2, the patient should hold dosing and topical treatment should be initiated by the ophthalmologist (according to treatment guidelines below). When the event is CTCAE grade ≤ 1, dosing of trial drug should not be further reduced but resumed at 0.9 mg/kg.
- CTCAE grade ≥ 3 conjunctivitis: Hold dosing. Topical treatment should be initiated by the ophthalmologist (according to treatment guidelines below). When the event has improved to CTCAE grade ≤ 1, dosing of trial drug can be resumed at a reduced dose (please refer to dose modification scheme below).
 - o If the conjunctivitis recurs at CTCAE grade ≥ 3 , the patient must permanently discontinue treatment with trial drug.

Keratitis:

Grading: All events of keratitis should be graded according to both:

- Ophthalmological grading based on the objective eye-examination findings performed by the ophthalmologist.
- CTCAE grading system based on NCI-CTCAE criteria assessed by the investigator (CTCAE version 4.03).

Dose delay and dose modification:

- CTCAE grade ≤ 2 keratitis: Hold dosing until the event is managed effectively by topical treatment (according to treatment guidelines below) initiated by the ophthalmologist. When the event is ≤ CTCAE grade 1, dosing of trial drug can be resumed at a reduced dose (please refer to dose modification scheme below).
 - o In case of recurrence of CTCAE grade ≤ 2 keratitis, the patient should hold dosing and topical treatment (according to treatment guidelines below) should be initiated by the ophthalmologist. When the event is CTCAE grade ≤ 1 , dosing of trial drug can be resumed at a further reduced dose (please refer to dose modification scheme below).
 - In case of 3^{rd} occurrence of keratitis CTCAE grade ≤ 2 , the patient must permanently discontinue treatment with trial drug.
- CTCAE grade ≥ 3 keratitis: The patient must permanently discontinue treatment with trial drug.

Final 5.0 (incorporating Protocol Amendment 4) 06 Jul 2017

Conjunctival ulceration:

If an ophthalmological evaluation reveals fluorescent patches or conjunctival ulceration of any grade:

- Hold dose until conjunctivitis/conjunctival ulceration is managed effectively by topical treatment (according to treatment guidelines below). When the event is managed effectively, dosing of trial drug can be resumed at a reduced dose (please refer to dose modification scheme below).
- o If symptoms do not stabilize/improve after dose reduction, the patient must permanently discontinue treatment with trial drug.

Treatment guidelines

_	
Ocular symptom	Treatment guideline (The length of treatment should be decided by the local ophthalmologist)
Conjunctivitis: CTCAE grade 1	The local ophthalmologist should prescribe frequent dosing of preservative-free topical steroid drops
Conjunctivitis: CTCAE grade 2	The local ophthalmologist should prescribe frequent dosing (every 2nd hour) of preservative-free topical steroid drops in conjunction with preservative free antibiotic prophylaxis such as chloramphenicol
Conjunctivitis: CTCAE grade 3	The local ophthalmologist should prescribe frequent dosing (every 2nd hour) of preservative-free topical steroid drops in conjunction with preservative free antibiotic prophylaxis such as chloramphenicol
Keratitis: CTCAE grade 1	The local ophthalmologist should prescribe frequent dosing of preservative-free topical steroid drops
Keratitis: CTCAE grade 2	The local ophthalmologist should prescribe frequent dosing (every 2nd hour) of preservative-free topical steroid drops in conjunction with preservative free antibiotic prophylaxis such as chloramphenicol
Conjunctival ulceration: any grade	The local ophthalmologist should prescribe frequent dosing (every 2nd hour) of preservative-free topical steroid drops in conjunction with preservative free antibiotic prophylaxis such as chloramphenicol

Final 5.0 (incorporating Protocol Amendment 4)
06 Jul 2017

Dose modification scheme:

Previous dose of tisotumab vedotin	Reduced dose of tisotumab vedotin	
2.0 mg/kg	1.3 mg/kg	
1.3 mg/kg	0.9 mg/kg	
0.9 mg/kg	0.9 mg/kg*	

^{*}If the patient is already being treated with tisotumab vedotin (HuMax-TF-ADC) 0.9 mg/kg every 3rd week, the dose of tisotumab vedotin (HuMax-TF-ADC) should not be reduced further.

Trial drug discontinuation criteria for ocular toxicity:

Treatment with trial drug must be permanently discontinued in case of:

- First recurrence of CTCAE grade ≥ 3 conjunctivitis (despite dose reduction)
- Third recurrence of CTCAE grade ≤ 2 keratitis (despite dose reductions)
- First occurrence of CTCAE grade \geq 3 keratitis
- Ophthalmological evaluation reveals conjunctival/corneal scarring
- Any grade of symblepharon
- Any grade of fluorescent patches or conjunctival ulceration that does not stabilize or improve after dose reduction
- Any dose delay related to ocular toxicity exceeding 12 weeks

